9.3 Safety

The Safety population includes all randomized patients who received at least one dose of investigational treatment. The Safety population will be analyzed as treated and will be used for the safety analyses. No data will be excluded for any reason.

10. Patient Disposition

Patient disposition will be presented in terms of the numbers and percentages of patients who were randomized. Patients who are not discontinued from the study will be considered study completers.

The total number of screened subjects with the number and percentage of screen failure subjects and reasons for screen failure will be displayed with the percentages calculated using total number of 13/FEB/2014 Confidential Page 12 of 21

Statistical Analysis Plan Protocol RTA 408-C-1307

Version 1.0

screen failures as the denominator. The number of patients in each of the populations (ITT, PP and Safety) will be displayed by treatment and percentages will be calculated using randomized patients as the denominator.

The number and percentage of patients with major protocol deviations will be summarized by treatment group for all randomized patients. The protocol deviations that will be summarized include: non-compliance with any scheduled study visit, non-compliance with study treatment, use of disallowed concomitant medications, non-compliance with study inclusion or exclusion criteria, non-compliance with study assessment procedures and other. A patient listing will be provided that includes the date of the deviation, the deviation description and the classification of whether the deviation was judged to be major or minor.

The number and percentage of patients prematurely discontinued from study treatment and the reasons for study treatment discontinuation will be summarized by treatment group for all randomized patients. The reasons for study treatment discontinuation that will be summarized include: adverse event (AE), protocol violation, lack of efficacy, administrative reasons, sponsor termination of study, voluntary withdrawal, pregnancy and other. A patient listing will be provided that includes the date of and reason for premature study treatment discontinuation.

The number and percentage of patients prematurely discontinued from the study and the reasons for study discontinuation will be summarized by treatment group for all randomized patients. The reasons for study discontinuation that will be summarized include: adverse event (AE), protocol violation, lack of efficacy, administrative reasons, sponsor termination of study, voluntary withdrawal, pregnancy and other. A patient listing will be provided that includes the date of and reason for premature study discontinuation.

In addition, patient listings will be provided that include informed consent date, inclusion and exclusion criteria violations, and exclusions from the PP population.

11. Demographic and Baseline Characteristics

The demographic variables collected in this study include age, gender, race, ethnicity and iris color. Patients who record more than one race will be grouped into a single category denoted as multi-racial. Demographic variables will be summarized for each of the analysis populations separately.

Age (years) will be summarized, overall and by treatment, using number of observations, mean, standard deviation, median, minimum and maximum values. Age will also be categorized as follows: <65 years and ≥65 years. Age will be reported in years and calculated using the following formula:

Age = ((informed consent date - date of birth) +1 / 365.25) truncated as an integer

Statistical Analysis Plan Protocol RTA 408-C-1307

Version 1.0

The number and percentage of patients will be presented, overall and by treatment, for age category, gender, race, ethnicity and iris color (for the study eye only).

A patient listing that includes all demographic variables will be provided.

12. Medical History and Concomitant Medications

12.1 Medical History

Medical history will be coded using the Medical Dictionary for Regulatory Activities (MedDRA), version 16.1.

Non-ocular medical history will be summarized using discrete summary statistics and presented overall and by treatment group at the patient and event level by System Organ Class (SOC) and Preferred Term (PT) using the ITT population. Ocular medical history will be similarly summarized at the patient level, separately for the study eye and fellow eye. If a patient reports the same PT multiple times within the same SOC, that PT will only be reported once within that SOC. As with the PT, if a patient reports multiple conditions within the same SOC, that SOC will only be reported once. Listings of medical history will be generated.

12.2 Prior and Concomitant Medications

Prior and concomitant medications will be coded using World Health Organization Drug Dictionary Enhanced (WHO DDE; Enhanced B2, September 2013) and summarized to the therapeutic drug class (Anatomical Therapeutic Chemical (ATC) 4 classification) and generic term.

Prior medications are defined as those medications listed as having been taken with a stop date prior to study drug administration. Concomitant medications are defined as those medications listed as having been taken 1) prior to study drug administration and continuing for any period of time following the first administration of study drug or 2) at any time following the first administration of study drug.

Prior and concomitant medications will be summarized using the ITT population. Medications will be tabulated for each treatment group using frequencies and percentages, with separate tables for non-ocular, study eye, and fellow eye medications. Patients may have more than 1 medication per ATC4 text. At each level of patient summarization, a patient will be counted once if he/she reports 1 or more medications. Percentages will be based on the number of patients in each treatment group. The listing for prior and concomitant medications will include the start and stop dates as well as the date of the first administration of study drug to facilitate identification of whether a medication was a prior or concomitant medication.

13. Dosing Compliance and Treatment Exposure

13.1 Dosing Compliance

Dosing compliance (% compliance) will be assessed by calculating the number of actual doses received and comparing that to the number of expected doses as follows:

Statistical Analysis Plan Protocol RTA 408-C-1307

Version 1.0

Compliance (%) = Number of Actual Doses Received
Number of Expected Doses x 100%

The number of actual doses received will be calculated from the number of expected doses - the number of missed doses recorded in the CRF and determined through review of the patient diary and the in-office instillations. The number of expected doses that will be used for calculating compliance will be calculated as 2x[(date of last dose - date of Visit 2 [Day 1]) +1] for all patients, regardless of study completion status.

A categorical dosing compliance variable will also be derived as compliant (≥75%) and non-compliant (<75%).

Dosing compliance (%) will be summarized using number of observations, mean, standard deviation, median, minimum and maximum for each treatment group. The compliance category defined above will be summarized with counts and percentages. A patient listing of dosing compliance will also be produced.

13.2 Treatment Exposure

Extent of treatment exposure will be calculated in days using the following:

Extent of Exposure (days) = (Date of last dose - date of Visit 2 [Day 1]) + 1

Extent of treatment exposure (days) for each patient exposed to study drug will be summarized using descriptive statistics for each treatment group. A patient listing of treatment exposure will also be produced.

14. Efficacy Analyses

14.1 Primary Analysis

The anterior chamber cell grade for all study eyes will be recorded as well as the anterior chamber cell count if the actual number of cells observed is 10 cells or fewer (only white blood cells should be counted; red blood cells and pigment cells should not be counted). The 5-unit grading scale for anterior chamber cells is from 0 to 4 where 0 = 0 cells, 1 = 1 to 10 cells, 2 = 11 to 20 cells, 3 = 21 to 50 cells and 4 = >50 cells.

Ocular pain will be assessed by the patient utilizing a Numerical Pain Rating Scale (NPRS) graded from 0 to 10. Patients will assess the level of pain they are experiencing in the study eye at the time of the assessment.

[figure not shown]
The examiner will ask the patient the following question in reference to Figure 1 and will record the number selected by the subject on the appropriate eCRF.

Statistical Analysis Plan Protocol RTA 408-C-1307

Version 1.0

On a scale of 0 to 10, in which 0 is no pain and 10 is the worst possible or unbearable pain, please mark on the scale the number that best describes the pain or discomfort you are feeling in the operated* eye at this time. The middle of the scale (around 5) can be used to describe "moderate pain".

The proportion of study eyes with absence of anterior chamber cells and the proportion of study eyes with absence of ocular pain will be presented overall and by treatment group using categorical summary statistics, including 90% confidence intervals.

Additionally, 80% and 95% confidence intervals will be constructed around the difference in proportions for each primary outcome using asymptotic normal approximations. Pearson's chi-square tests will be employed for statistical inference testing. Fisher's exact tests and exact confidence intervals will be employed in cases of expected counts less than five.

Additionally, a Cochran-Armitage test will be used to test for trend separately in the proportion of study eyes with absence of anterior chamber cells and the proportion of study eyes with absence of pain with increasing active concentration, using all three treatment groups.

The ITT population will be used for the primary analyses. In addition, confirmatory analyses will be performed on the PP population. The primary analysis variables will be presented in patient listings.

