Summary of Visit Schedule:	 Visit 1, Day ≥ -28: Screening, Baseline Evaluation Visit 2, Day 1 (24 ± 6 hours post-surgery): Study enrollment, Randomization, and 1st Study Drug Dose Visit 3, Day 4 (± 1): On Treatment Follow-up; Inflammation and Pain Assessments Visit 4, Day 8 (± 1): On Treatment Follow-up; Inflammation and Pain Assessments Visit 5, Day 15 (+ 1): Inflammation and Pain Assessments after End of Treatment Visit 6, Day 21 (± 1): Post-Treatment Follow-up; Exit Visit
Measures Taken to Reduce Bias:	Randomization will be used to avoid bias in the assignment of patients to treatment, to increase the likelihood that known and unknown patient attributes are evenly balanced across treatment groups, and to enhance the validity of statistical comparisons across treatment groups. Masked treatment will be used to reduce potential bias during data collection and evaluation of clinical endpoints.

ſ

٦

Study Population Characteristics		
Number of Patients:	Approximately 105 patients will be enrolled in this study to complete 93 patients: 31 per arm	
Condition/Disease:	Inflammation and pain following ocular surgery	
Inclusion Criteria:	 Patients must: 1. Have provided written informed consent, approved by the appropriate institutional review board; 2. Be able to comply with study requirements and visit schedule; 3. Be greater than or equal to 18 years of age of either sex or any race; 4. Have undergone unilateral cataract extraction via phacoemulsification and posterior chamber intraocular lens (PCIOL) implantation in the study eye on the day prior to study enrollment/randomization; 5. Have a grade of ≥ 2 in anterior chamber cell score on day after surgery (Day 1) in the study eye; 6. Have a potential post-operative pin-hole visual acuity (VA) < 1.0 logarithm of the minimum angle of resolution (logMAR) in the operative eye and fellow eye as measured using an Early Treatment for Diabetic Retinopathy Study (ETDRS) chart; 7. (For females of childbearing potential) agree to have urine pregnancy testing performed at screening (must be negative) and at exit visit; must not be lactating; and must agree to use a medically acceptable form of birth control¹ throughout the study duration. Women of childbearing potential include all females who have experienced menarche and have not experienced menopause (as defined by 	

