5 STUDY POPULATION

5.1 Number of Patients

Approximately 105 patients will be enrolled in this multi-center study, 35 per arm, in order to complete 31 patients per arm.

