5.3 Inclusion Criteria

Each patient must meet the following criteria:

- 1. Have provided written informed consent, approved by the appropriate institutional review board;
- 2. Be able to comply with study requirements and visit schedule;
- 3. Be greater than or equal to 18 years of age of either sex or any race;
- 4. Have undergone unilateral cataract extraction via phacoemulsification and posterior chamber intraocular lens (PCIOL) implantation in the study eye on the day prior to study enrollment/randomization;
- 5. Have a grade of ≥ 2 in anterior chamber cell score on day after surgery (Day 1) in the study eye;

- 6. Have a potential post-operative pin-hole visual acuity (VA) < 1.0 logarithm of the minimum angle of resolution (logMAR) in the operative eye and fellow eye as measured using an Early Treatment for Diabetic Retinopathy Study (ETDRS) chart;
- 7. (For females of childbearing potential) agree to have urine pregnancy testing performed at screening (must be negative) and at exit visit; must not be lactating; and must agree to use a medically acceptable form of birth control² throughout the study duration. Women of childbearing potential include all females who have experienced menarche and have not experienced menopause (as defined by amenorrhea for greater than 12 consecutive months) or have not undergone successful surgical sterilization (hysterectomy, bilateral tubal ligation, or bilateral oophorectomy).

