10.10 Primary Efficacy Analyses

The primary efficacy variables, study eyes with absence of anterior chamber cells at Visit 5 (Day 15) and study eyes with absence of pain at Visit 3 (Day 4), will be summarized using discrete summary statistics, including 90% asymptotic normal confidence intervals for each treatment group. The primary efficacy analyses will first test the difference in proportion of study eyes with a grade of '0' in anterior chamber cells between the 1.0% concentration of RTA 408 Ophthalmic Suspension and placebo and between the 0.5% concentration of RTA 408 Ophthalmic Suspension and placebo at Visit 5 (Day 15) using the Pearson chi-squared statistic.

If the proportion of patients with a grade of '0' for anterior chamber cells is statistically significantly higher for the 1.0% concentration versus placebo at a 1-sided alpha=0.10, then the hierarchical hypothesis testing will compare the proportion of patients with absence of ocular pain at Visit 3 (Day 4) between the 1.0% concentration of RTA 408 Ophthalmic Suspension and placebo using the Pearson chi-squared statistic at a 1-sided alpha=0.10.

If the proportion of patients with a grade of '0' for anterior chamber cells is statistically significantly higher for the 0.5% concentration versus placebo at a 1-sided alpha=0.10, then the hierarchical hypothesis will compare the proportion of patients with absence of ocular pain at Visit 3 (Day 4) between the 0.5% concentration of RTA 408 Ophthalmic Suspension and placebo using the Pearson chi-squared statistic at a one-sided alpha=0.10.

Additionally, 95% confidence intervals will be constructed around the difference in proportions for each primary outcome using asymptotic normal approximations. Fisher's exact tests will be employed in cases of expected counts less than five.

If the test of the difference in the proportion of study eyes with absence of anterior chamber cells is statistically significant in favor of the 1.0% or 0.5% concentration of RTA 408 Ophthalmic Suspension versus placebo, then the study will be considered a success and the concentration(s) of RTA 408 Ophthalmic Suspension showing statistical significance will be declared to be superior to placebo in the proportion of study eyes with absence of anterior chamber cells at Visit 5 (Day 15).

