- H_{A22}: The difference, between study eyes treated with the 0.5% concentration of RTA 408 Ophthalmic Suspension and study eyes treated with placebo in the proportion of study eyes with absence of pain (score of 0) at Visit 3 (Day 4)≠ 0, with superiority claimed if the difference is greater than 0 (RTA 408 Ophthalmic Suspension Placebo).

5. Sample Size and Power Considerations

Statistical Analysis Plan Protocol RTA 408-C-1307

SIGNIFICANTLY DIFFERENT

Version 1.0

The primary analyses will first test the difference in the proportion of patients with absence of anterior chamber cells in the study eye between the 1.0% concentration of RTA 408 Ophthalmic Suspension and placebo and between the 0.5% concentration of RTA 408 Ophthalmic Suspension and placebo at Visit 5 (Day 15) using the Pearson chi-squared statistic at a 1-sided alpha=0.10.

If the proportion of patients with a grade of '0' for anterior chamber cells is statistically significantly higher for the 1.0% concentration versus placebo at a 1-sided alpha=0.10, then the hierarchical hypothesis testing will compare the proportion of patients with absence of ocular pain at Visit 3 (Day 4) between the 1.0% concentration of RTA 408 Ophthalmic Suspension and placebo using the Pearson chi-squared statistic at a 1-sided alpha=0.10.

If the proportion of patients with a grade of '0' for anterior chamber cells is statistically significantly higher for the 0.5% concentration versus placebo at a 1-sided alpha=0.10, then the hierarchical hypothesis will compare the proportion of patients with absence of ocular pain at Visit 3 (Day 4) between the 0.5% concentration of RTA 408 Ophthalmic Suspension and placebo using the Pearson chi-squared statistic at a one-sided alpha=0.10.

If the test of the difference in the proportion of study eyes with absence of anterior chamber cells is statistically significant in favor of the 1.0% or 0.5% concentration of RTA 408 Ophthalmic Suspension versus placebo, then the study will be considered a success and the concentration(s) of RTA 408 Ophthalmic Suspension showing statistical significance will be declared to be superior to placebo in the proportion of study eyes with absence of anterior chamber cells at Visit 5 (Day 15).

6. General Statistical Consider	rations			
All data analysis will be performe	d by	ter the study is completed		
and the database has been locked and released for un-masking. Statistical programming and				

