analyses will be performed using	SAS® Version 9.2 or higher. Outp	out will be provided in RTF format		
for tables and PDF format for tab	les, listings, and figures. All study	data will be listed by patient,		
treatment, and visit (as applicable	∍).			
13/FEB/2014	Confidential	Page 7 of 21		

Statistical Analysis Plan Protocol RTA 408-C-1307

Version

1.0

SIGNIFICANTLY DIFFEREN

Continuous and ordinal variables will be summarized using descriptive statistics (i.e., number of observations (n), arithmetic mean, standard deviation (SD), minimum, median, and maximum). Categorical variables will be summarized descriptively using counts and percentages. Means and medians will be rounded to one decimal more than the collected data; SDs will be rounded to two decimal place more than the collected data. All percentages will be rounded to one decimal place

Unless otherwise specified, summaries will be presented by treatment group and visit. The baseline measure is defined as the last non-missing measure prior to initiation of investigational treatment, which is Visit 2 (Day 1) for all measures with the exception of the dilated indirect ophthalmoscopic examination where the Visit 1 (\geq 28 days prior to surgery) will serve as baseline. Differences between active treatment groups and placebo will be calculated as Active minus Placebo. Changes from baseline will be calculated as follow-up value minus baseline value. All statistical tests will be one-sided with a significance level of 0.10 (α = 0.10). Confidence intervals (CI) for differences between treatment groups will be two-sided at 80% confidence as well as 95% confidence. All p values will be rounded to four decimal places; p values less than 0.0001 will be presented as "< 0.0001"; p values greater than 0.9999 will be presented as ">0.9999".

All study data will be listed by patient, treatment, and visit (as applicable), based on all enrolled patients.

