6.2 Adjustments for Multiplicity

To address the two primary efficacy variables employed in this study, the primary efficacy variables have been prioritized into a hierarchical structure. In order to test ocular pain for RTA Ophthalmic Suspension 1.0%, anterior chamber cells must have shown statistically significant improvements for RTA Ophthalmic Suspension 1.0% versus placebo using a one-sided significance level of 0.10. This same strategy is applicable to the 0.5% concentration of RTA Ophthalmic Suspension.

No multiplicity adjustments will be employed for the multiplicity of tests due to two concentrations of active.

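### The Day 15 cell-clearance tests that alone decide study success ignore the Day 1 cell grade; a test stratified by grade would hold its error rate in an imbalanced trial at almost no cost

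*SAP*

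**What the plan says.** **Test.** Protocol 10.10 and SAP 14.1 compare each concentration with placebo on the proportion of study eyes with no cells at Day 15. The SAP states that "Pearson's chi-square tests will be employed for statistical inference testing", with Fisher's exact test and exact intervals where expected counts fall below five. No stratum or covariate is named. SAP section 6 sets the level: "All statistical tests will be one-sided with a significance level of 0.10".

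**Success rule.** If either concentration is significant on this endpoint, "then the study will be considered a success" (Protocol 10.10; SAP section 5 has the same rule). Pain at Day 4 is tested only for a concentration that has passed and does not enter the rule. SAP 6.2 adds: "No multiplicity adjustments will be employed for the multiplicity of tests due to two concentrations of active".

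**Baseline.** Inclusion criterion 5 in Protocol 5.3 reads: "Have a grade of ≥ 2 in anterior chamber cell score on day after surgery (Day 1) in the study eye". On the Appendix 1 scale this admits grade 2 (11-20 cells), grade 3 (21-50) and grade 4 (more than 50). The grade is an entry criterion, so it is recorded for every eligible patient before randomization.

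**Randomization and other analyses.** SAP 7.3 uses site-specific kit lists in blocks of six, with no stratification by grade. The sensitivity analyses in SAP 6.3 concern missing data only. Protocol 10.13 plans no subgroup analyses. Cell grade otherwise appears in by-visit and change-from-baseline summaries (SAP 14.2, Table 14.2.3.1) and in a patient listing.

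**The concern.** The endpoint is zero cells on the same scale that defines the starting grade. It is therefore plausible, though the documents do not show it, that an eye starting above 50 cells clears less often by Day 15 than one starting at 11-20.

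With about 35 patients per arm, the share of high-grade eyes can differ between arms by chance. If grade is prognostic, the unadjusted comparison carries that difference into tests 1a and 1b, where it can help an inactive drug or hide an active one. Both tests share one placebo arm, so an atypical placebo arm moves them in the same direction. Even in balanced trials, the unadjusted test leaves explainable variation in the error term and gives up some power.

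**Working it through.** **Plan figures.** "Approximately 105 patients will be enrolled in this multi-center study, 35 per arm, in order to complete 31 patients per arm". Check: 3 × 35 = 105 and 3 × 31 = 93. The sample-size text is not legible in the public documents, so planned power cannot be reproduced. I use 35 per arm because the primary analysis is intent-to-treat with imputation. For scale, 31 per arm at one-sided 0.10 detects a difference of 22-27 points with 80% power for placebo rates of 10-40%.

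**Step 1: how often the arms differ.** Let q be the share of eyes at grade 3-4 (assumed). The SD of the between-arm difference is √(2q(1−q)/35): 0.110 at q = 0.3 and 0.120 at q = 0.5. Since 5/35 = 14.3% and 6/35 = 17.1%, a gap of at least 15 points means six or more patients. The exact binomial probability in either direction is 15.1% at q = 0.3 and 18.8% at q = 0.5. By symmetry, half of that favours active: 7.5% and 9.4%.

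**Step 2: hand check of the consequence.** Take no drug effect, q = 0.5 and clearance of 40% (grade 2) and 10% (grade 3-4), which is 25% overall. A six-patient gap shifts the expected difference by 6/35 × 30 = 5.1 points. The standard error is √(2 × 0.25 × 0.75/35) = 0.1035, so the shift is about 0.50 SE. The rejection rate against 1.2816 becomes 1 − Φ(0.785) ≈ 22% if the gap favours active and 1 − Φ(1.778) ≈ 4% if it goes against. Averaging over gaps of six or more is somewhat more extreme (24.6% and 2.3% in the table).

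**Step 3: simulation.** 200,000 trials per scenario, 35 per arm, one active arm against placebo.
- Pearson: z = (p₁ − p₀)/√(2p̄(1 − p̄)/35).
- Cochran-Mantel-Haenszel (CMH): z = Σ(y₁ₖ − m₁ₖtₖ/Nₖ)/√Σ[m₁ₖm₀ₖtₖ(Nₖ − tₖ)/(Nₖ²(Nₖ − 1))], summed over grade 2 and grade 3-4. In stratum k, y₁ₖ is active clearances, m₁ₖ and m₀ₖ are the arm sizes, and tₖ is total clearances among Nₖ eyes.
- Reject if z > 1.2816. The Fisher fallback was not simulated.

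Main set of assumptions, none from the documents: odds ratio 2.5; 10-50% of eyes at grade 3-4; placebo clearance 15% in those eyes and 0-40 points higher in grade 2 eyes.
- Gap of 20-40 points, 30-50% high grade: power 58-67% (Pearson) against 66-70% (CMH), a gain of about 2.5-7.5 points.
- Gap of 20 points, 20% high grade: +2.3 points.
- Gap of 10 points, 10-50% high grade: −0.3 to +0.5 points.
- No gap: a change of less than 1 point.
- No drug effect, 20-40 point gap, 30-50% high grade, imbalance of 15 points or more: Pearson rejects in about 18-27% when it favours active (repeat runs put the lower end at 18 or 19) and in about 1-5% when it goes against. CMH is about 10% in both.
- True effect, imbalance against active: Pearson power about 27-51%, CMH 65-69%.

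Second set, as a cross-check (odds ratio 3, other clearance rates; all figures %). 'For' and 'against' mean an imbalance of at least 15 points favouring or opposing active.

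| Share grade 3-4 | Placebo clearance, grade 2 / 3-4 | Pearson false positives: all / for / against | CMH false positives: for / against | Power: Pearson → CMH |
|---|---|---|---|---|
| 30 | 25/25 | 10.3 / 10.4 / 9.9 | 10.3 / 9.7 | 80.9 → 81.1 |
| 30 | 30/20 | 10.3 / 13.9 / 7.1 | 9.9 / 10.3 | 80.7 → 81.7 |
| 30 | 30/10 | 10.3 / 19.4 / 4.3 | 10.1 / 10.1 | 76.4 → 79.0 |
| 50 | 40/10 | 10.3 / 24.6 / 2.3 | 9.9 / 10.1 | 70.2 → 75.9 |
| 50 | 50/10 | 10.3 / 29.9 / 1.2 | 10.1 / 9.9 | 65.3 → 74.4 |

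The pattern is the same. The last row, with the strongest link, gains 9.1 points.

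**The case against.** **A prespecified unadjusted test in a randomized phase 2 trial is legitimate.** This stands. The hypotheses are differences in proportions and Pearson tests them directly. A reader might infer that the overall type I error is inflated. It is not: it averages about 10% in every scenario.

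**The prognostic link is assumed.** This also stands. No section gives clearance by Day 1 grade or the share of eyes at grade 3-4. With a weak link the gain is about zero, so no minimum gain can be claimed. At 10% high grade, a 15-point imbalance occurs in only about 3% of comparisons, counting both directions.

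**The imbalance figures can be misread.** The 15-19% frequency counts both directions, while the raised false-positive rate belongs only to the favourable half. Pairing the two would overstate the risk.

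**An imbalance would be visible.** In part. The by-visit grade summary and the listing would show it, but nothing planned would adjust for it, and an adjustment chosen after unmasking carries little weight.

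**Stratifying thins the counts.** Correct, and it shapes the remedy. At a 30% share and 15% clearance, 35 × 0.30 × 0.15 ≈ 1.6 clearances are expected among high-grade placebo eyes. SAP 14.1's Fisher rule has no stratified counterpart. The 2 vs 3-4 cut is a choice; the documents do not supply it.

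What does not follow is that the change is mere preference. The stratified test holds its level in imbalanced trials and costs under 1 point of power if grade turns out not to matter.

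**Conclusion.** The point holds as a cheap improvement, not as an error in the plan. Tests 1a and 1b decide success and make no use of a baseline that is recorded in every patient before randomization and is not balanced by design.

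Under the main assumptions, stratifying is worth about 0 to +7.5 points of power. In the 30-50% share, 20-40 point gap range, a large favourable imbalance occurs in about 7.5-9.5% of comparisons, and an unfavourable one equally often. The first roughly doubles Pearson's false-positive rate or more; the second nearly removes false positives but cuts power to about 27-51%.

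These sizes depend on the link between Day 1 grade and Day 15 clearance, which the documents do not report. If there is no link, there is no problem and almost no cost. A reader might also take the result as a formal go/no-go decision. The documents say only that the study is considered a success, and they tie no development step to it. Because the planned power cannot be seen, the gain cannot be set against the design target.

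**What to change.** In SAP 14.1 and Protocol 10.10, before unmasking:

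1. Make the test for 1a and 1b a one-sided (0.10) Cochran-Mantel-Haenszel test stratified by Day 1 anterior chamber cell grade, 2 vs 3-4. Fix that grouping now.
2. Report the Mantel-Haenszel common risk difference with matching 80% and 95% intervals.
3. Replace the Fisher rule for these two tests with an exact conditional stratified test when counts are sparse, and write down the trigger.
4. Keep the unadjusted Pearson comparison as a named sensitivity analysis. State whether the Cochran-Armitage trend test stays unadjusted.
5. Tabulate Day 1 cell grade by arm with the baseline characteristics in SAP section 11.

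The cost is wording and one stratification variable; no new data are needed. The downsides are a slightly more complex estimate and under 1 point of power if grade is not prognostic. If the sponsor prefers to keep Pearson as primary, the minimum is to name the stratified test as a sensitivity analysis in advance and add the baseline table.
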